Primary objective	To study the effect of HCQ on pregnancy outcome in women with antiphospholipid antibodies.
Secondary objective	To collect blood samples for pharmacokinetic and biomarkers studies
Trial Design	A randomized controlled trial of HCQ versus placebo supplementing usual medication during pregnancy in women with antiphospholipid antibodies (aPL).
Endpoints	The primary endpoint is a composite of three principal aPL-related adverse pregnancy outcomes: one or more pregnancy loss(es) (either < 10 weeks gestation or beyond 10 weeks of gestation of a morphologically normal fetus documented by ultrasound or by direct examination of the fetus) and premature birth of a morphologically normal neonate before 34 weeks due to any of: pre- eclampsia, eclampsia, recognized features of placental insufficiency

	Premature birth for other reasons will not be included.
	The components of the primary endpoint will each be presented as secondary endpoints (below).
	 The pre-defined secondary endpoints include: Pregnancy loss < 10 weeks gestation Pregnancy loss > 10th week of gestation of a morphologically normal fetus documented by ultrasound or by direct examination of the fetus Premature birth of a morphologically normal neonate < 34 weeks due to any of: pre-eclampsia, eclampsia, recognized features of placental insufficiency. Gestational age at delivery Birth weight Delivery by Caesarean section Apgar score < 7 at 5 min Neonatal morbidity (bleeding or thrombotic complications, infections, congenital abnormalities) Days to hospital discharge following delivery (mother & child) Thrombotic events in the mother during pregnancy and 6 weeks post-partum. Days of neonate in special care Safety and tolerability of hydroxychloroquine in the mother and in the neonate
Sample Size	328 pregnant women (in order to achieve this number we will randomize 400 patients)
Summary of eligibility criteria	 Inclusion criteria: 1. Women with known aPL (i.e. isolated aPL or APS) who are planning pregnancy. aPL are defined by the presence of a positive test for anticardiolipin antibodies (IgG/IgM isotypes > 95th percentile) and/or lupus anticoagulant and/or anti- beta 2 glycoprotein-I (IgG/IgM isotypes > 95th percentile), on two or more consecutive occasions more than 12 weeks apart (a positive aPL test is defined under 'glossary and definitions'). The last positive test must be within 12 months of study entry. 2. Written informed consent to participate Exclusion criteria: 1. Women who are already pregnant
	 Allergy or adverse event to hydroxychloroquine. Hypersensitivity to the active substance, 4- aminoquinoline or any of the compounds of the IMP or placebo. Current treatment with hydroxychloroquine

	4. Age < 18 years and > 45 years
	5. Body weight < 45 kg
	6. Psoriasis
	7. Uncontrolled epilepsy
	8. Anti-Ro antibodies
	9. Renal replacement therapy
	 Other severe active co-morbidities (HIV, hepatitis B, severe gastrointestinal, neurological or blood disorders)
	11. Porphyria
	12. History of retinopathy or newly diagnosed retinopathy
	 History of galactose intolerance, lactase deficiency or glucose-galactose malabsorption
	14. History of glucose-6-dehydrogenase deficiency
	 Participation in any other IMP trial at the time of consent
	16. Previous pregnancy failure on hydroxychloroquine
IMP, dosage and route of administration	Treatment arm: Oral hydroxychloroquine 200 mg once daily in addition to usual care and medication starting from trial entry and throughout pregnancy until day of delivery.
	Placebo arm: placebo in addition to usual care and medication once daily starting from trial entry and throughout pregnancy until day of delivery.
Comparator product(s)	Placebo
Maximum duration of treatment of a Subject	 The maximum duration will include the timespan from entering the trial to time of conception and length of pregnancy. The total maximum length of treatment is 21 months.
	A maximum of 12 months treatment if a woman does not achieve pregnancy in this time period.
Version and date of protocol amendments	Previous version: Version 9.2, Date 31-JAN-2022 Version 9.3, Date 11-APRIL-2022

2. Glossary of Terms

Positive antiphospholipid (aPL) antibody test	 One of the following must be present on two occasions consecutively at least 12 weeks apart: Positive Lupus anticoagulant (LAC) by: aPTT, DRVVT, TSVT or Kaolin Anticardiolipin antibodies (aCL): IgG >95th percentile; IgM >95th percentile Anti-β2glycoproteinI (Anti-β2GPI): IgG >95th percentile; IgM >95th percentile The last positive test must be within 12 months prior to enrollment and local reference ranges must be provided.
Antiphospholipid syndrome (APS)	 The association of persistent positive antiphospholipid antibodies (at least 12 weeks apart) with venous and/or arterial thrombosis and/or microvascular thrombosis and/or pregnancy morbidity such as: (a) One or more unexplained deaths of a morphologically normal fetus at or beyond the 10th week of gestation, with normal fetal morphology documented by ultrasound or by direct examination of the fetus, or (b) One or more premature births of a morphologically normal neonate before the 34th week of gestation because of: (i) eclampsia or severe preeclampsia defined according to standard definitions, or (ii) recognized features of placental insufficiency, or (c) Three or more unexplained consecutive spontaneous abortions before the 10th week of gestation, with maternal anatomic or hormonal abnormalities and paternal and maternal chromosomal causes excluded [1].
Refractory obstetric APS	Women with persistent aPL who have experienced aPL related pregnancy complications despite treatment with aspirin and low molecular weight heparin.
Placental insufficiency	Generally accepted features of placental insufficiency include: (i) abnormal or non-reassuring fetal surveillance test(s), e.g. a non-reactive non-stress test, suggestive of fetal hypoxemia, (ii) abnormal Doppler flow velocimetry waveform analysis suggestive of fetal hypoxemia, e.g. absent end-diastolic flow in the umbilical artery, (iii) oligohydramnios, e.g. an amniotic fluid index of 5 cm or less, or (iv) a postnatal birth weight less than the 10th percentile for the gestational age (see definition of fetal growth restriction)
Fetal growth restriction (FGR):	 Fetal growth restriction as evidenced by an ultrasonographic estimated fetal weight based on Customized/population birth weight centile Birth weight <10th and <3rd customized/ population centile
Premature birth:	According to Gardosi [2, 3]. Birth between 24 weeks + 0 days and 36 weeks + 6 days weeks gestation.
Preeclampsia:	 Hypertension developing after 20 weeks gestation and the coexistence of one or more of the following new onset conditions: Proteinuria (spot urine protein/creatinine >30 mg/mmol [0.3 mg/mg] or >300 mg/day or at least 1 g/L ['2 + '] on dipstick testing) 2. Other maternal organ dysfunction: renal insufficiency (creatinine >90 umol/L) liver involvement (elevated transaminases and/or severe right upper quadrant or epigastric pain) neurological complications (examples include eclampsia, altered mental status, blindness, stroke, or more commonly hyperreflexia when accompanied by clonus, severe headaches when accompanied by hyperreflexia, persistent visual scotomata) haematological complications (thrombocytopenia, DIC, haemolysis) Uteroplacental dysfunction

Eclampsia:	Onset of seizures in pregnant women with pre-eclampsia.					
Gestational age	Measure of the age of a pregnancy measured in weeks, from the first day of the woman's last menstrual cycle to the current date.					
Apgar score	A routinely used measure of the physical condition of a newborn infant. It is obtained			0	1	2
	by adding points (2, 1, or 0) for heart rate,		HR	Absent	<100	>100
	respiratory effort, muscle tone, response to stimulation, and skin coloration performed on a baby at 1 and 5 minutes after birth; a		Respiration	Absent	Irregular/ weak cry	Strong cry
	score of ten represents the best possible condition (The Apgar scoring system is shown to the right).		Reflex irritability	No response	Grimace	Cough/ sneeze
		- 1	Muscle tone	None	Some flexion	Well flexed
			Color	Central cyanosis	Peripheral cyanosis	Pink
Demographic information	 Please record one of the following: British European, Pakistan, India, Poland, Bangladesh, Caribbean, Ireland, Chinese, Somalia, Iraq, Zimbabwe, Nigeria, Afghanistan, the Netherlands (Dutch European), Morocco, Turkey, Suriname, Antiles/Aruba, Germany, Ghana, Indonesia, Italy, Egypt, Romania, Albania, other North African, Peru, Philippines, Ecuador, Ukraine, Denmark, Sweden, Norway, Albania, Lebanon, Bosnia-Herzegovina, Other. 					

CONTENTS

1.Protocol Synopsis	
2. Glossary of Terms	
3.Background & Rationale	
4. Trial Objectives and Design	.12
4.1. Trial Objectives	.14
4.1.1 Primary Endpoints	.15
4.1.2 Secondary Endpoints	.15

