4.3 Trial Flowchart

HYPATIA trial study procedures

	Pre-pregnancy		Pregnancy			Post- partum	
	Screening visit*	Baseline visit*	Pre- pregnancy visits §	1st Trimester	2nd Trimester	3rd Trimester	Post- partum visit†
Written informed consent	x	-					
Demographics	x						
Eligibilty assessment (1)	x	x					
Past medical history (2)	x						
Smoking history	x				x		
Past pregnancy history (3)	x						
Current medication	x	x	x	x	x	x	x
Height	x	~	~	~	~	~	~
Weight	x						
- · · · · · · · · · · · · · · · · · · ·							
Collection of blood results (4)	X						
Blood pressure & Pulse	X						
Urine dip	X						
Randomisation		X					
Dispensation IMP		X	X	X	X	X	
Adverse events monitoring		X	X	X	X	X	X
Physical exam (incl stetoscopy)	X		X	x	X	X	
Blood sample (5)	X		X	X	X	X	
Info about current pregnancy (6)			~	X	X	X	
Compliance check (7) Blood for additional research (8)		×	X	x x	X	x	x
Growth scans		X	X	*	x x	x	X
Uterine Artery Doppler (20-24 weeks)					x (9)	^	^
Child gender					× (9)		x
Birth date							x
Child APGAR at 5 min							x
Days of admission (mother&child)							x
Gestational age							x
Mode of delivery (Cesarean Y/N)							x
Birth weight							x
Neonatal morbidity (neonatal bleeding or thrombotic complications, infections, congenital abnormalities, days in neonatal special care)							x
* These visits can all be completed on the same	day. Consen	t within 3 mo	onths.				
§ Visits every 3 months until patient pregnant, th max 4 times (a total of 12 months)	en new dispe	nsation of s	tudy drug and	dispensation	every 3 mor	nths. Pre-preg	nancy visits
† Follow up visit should be completed within 6 we can contact the participant to obtain the study inf		atient is una	ble to attend c	linic within th	e timeframe	of 6 weeks, tl	ne study team
(1) Eligibility assessment: persistent presence of	aPL twice 12	2 weeks apa	rt, ENA negati	ve			
(2) Past medical history as per exclusion criteria other significant past medical history. Blood sam antibodies. Blood results can be obtained from re screening as per standard of care.	nple review (F	BC, kindne	y and liver pro	file) and resu	Its will be co	llected: aPL a	ntibodies, ENA
 (3) Past pregnancy history - to record in chronolo premature birth < 34 due to pre-eclampsia, eclar 						s, miscarriag	e > 10 weeks,
(4) max 12 months old (antiphospholipid antibod	ies (aPL) type	e and titres i	incl local cut of	f, ENA antibo	odies). Repe	at aPL if need	led.

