5.7 Concomitant Medication

We are proposing a study of hydroxychloroquine in addition to their usual medication in women with underlying aPL who are planning pregnancy. As with chloroquine, antacids may reduce absorption of hydroxychloroquine, so we advise a four hour interval between the IMP and the intake of any antacids. As hydroxychloroquine may enhance the effects of a hypoglycaemic treatment, a decrease in doses of insulin or antidiabetic drugs may be required.

All patients will very likely be on some form of medications prior to entering this trial, which may include aspirin, heparin, in some particular cases warfarin or immunosuppressant medications such as azathioprine. (Warfarin may be used as secondary thrombosis prevention, however, once they have a positive pregnancy test, the warfarin will be stopped and they switched to low molecular heparin according to usual medical practice). An individual assessment will be made prior to entering the trial. None of those drugs are contraindicated as concomitant therapy with hydroxychloroquine. All drugs patients are taking will be recorded at every visit in the patient CRF. This information includes drug type, strength, how long the medication was taken for and the indication.

Patients participating in this trial will either be planning for or be pregnant. All medications absolutely contraindicated in pregnancy should be avoided after pregnancy is confirmed. In this particular patient group this may for example include anticoagulation treatment (such as warfarin) or certain types of blood pressure medications.

6 Selection and Withdrawal of Subjects

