8.1.1 Primary Efficacy Parameters

The primary efficacy parameters will include the absence of pregnancy complications, i.e. as defined in the primary endpoint is defined as follows:

The primary endpoint is a composite of three principal aPL-related adverse pregnancy outcomes: one or more pregnancy loss(es) (either < 10 weeks gestation or beyond 10 weeks of gestation of a morphologically normal fetus documented by ultrasound or by direct examination of the fetus) and premature birth of a morphologically normal neonate before 34 weeks due to any of: pre-eclampsia, eclampsia, recognized features of placental insufficiency Premature birth for other reasons will not be included.

The components of the primary endpoint will each be presented as secondary endpoints (below).

The pre-defined secondary endpoints include:

- 1. Pregnancy loss < 10 weeks gestation
- Pregnancy loss > 10th weeks of gestation of a morphologically normal fetus documented by ultrasound or by direct examination of the fetus
- 3. Premature birth of a morphologically normal neonate < 34 weeks due to any of: pre-eclampsia, eclampsia, recognized features of placental insufficiency.
- 4. Gestational age at delivery
- 5. Birth weight
- 6. Delivery by Caesarean section
- 7. Apgar score < 7 at 5 min
- 8. Neonatal morbidity (bleeding or thrombotic complications, infections, congenital abnormalities)
- 9. Days to hospital discharge following delivery (mother & child)
- 10. Thrombotic events in the mother during pregnancy and 6 weeks post-partum.
- 11. Days of neonate in special care
- 12. Safety and tolerability of hydroxychloroquine in the mother and in the neonate

The components of the primary endpoint will each be presented as secondary endpoints.

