8.2 Procedures for Assessing Efficacy Parameters

The primary outcome of the HYPATIA study will be a composite of pregnancy complications as defined above (see primary and secondary outcomes).

Adverse pregnancy outcomes are defined under 'Glossary and Definition' (Section 2). Each adverse pregnancy outcome will be recorded for each individual case. Fetal growth will be assessed by using standardized ultrasound methods. Pre-eclampsia will be diagnosed according to international criteria (see definition in section 2), information with regards to the baby, i.e. gestational age at delivery, birth weight, mode of delivery, Apgar < 7 at 5 min, neonatal morbidity (bleeding or thrombotic complications, infections, congenital abnormalities), number of days in hospital and thrombotic events in the mother during the puerperium. Patients will be consented to give the trial team access to their child's hospital notes if needed (i.e. in case of admission to paediatric special care units or complications such as intraventricular haemorrhage).

Symptoms suggestive of VTE will be evaluated according to the usual diagnostic methods. Patients who present with symptoms suggestive of stroke, myocardial infarction or arterial thrombosis at other sites, generally present as a clinical emergency and clinical and diagnostic information will be obtained retrospectively from the center at which they have been managed.

Efficacy makers are defined as follows:

Miscarriage: The presence of a miscarriage will be determined due to standard medical practice at each participating unit. Usually this will include a history from the patient and at some centers ultrasound for confirmation.

Fetal death: This will be determined by ultrasound according to standard medical practice.

Intrauterine growth restriction: Serial ultrasound assessments according to standard medical practice and the use of growth percentiles will be used to determine the presence or absence of fetal growth restriction (individualized birth weight according to Gardosi).

Placental abruption: Patient history and ultrasound according to standard medical practice.

Premature birth: Birth between 24+0 and 36+6 weeks gestation.

Pre-eclampsia as defined in international guidelines [4]: Hypertension developing after 20 weeks gestation and the coexistence of one or more of the following new onset conditions:

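### The pre-eclampsia definition has no rule for hypertension present before 20 weeks, so a birth before 34 weeks for superimposed pre-eclampsia may drop out of the primary endpoint unless placental insufficiency was also a cause

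*Protocol*

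**What the plan says.** Section 8.1.1 of the Protocol counts as a primary-endpoint event a "premature birth of a morphologically normal neonate before 34 weeks due to any of: pre-eclampsia, eclampsia, recognized features of placental insufficiency". It adds: "Premature birth for other reasons will not be included". Success is the reverse of the composite: "The primary efficacy parameters will include the absence of pregnancy complications".

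The glossary (section 2) defines pre-eclampsia as "Hypertension developing after 20 weeks gestation and the coexistence of one or more of the following new onset conditions", followed by proteinuria, other maternal organ dysfunction and uteroplacental dysfunction. Section 8.2 says "Pre-eclampsia will be diagnosed according to international criteria (see definition in section 2", cites an international guideline, and then prints the same wording again. Eclampsia is defined in the glossary as seizures in women with pre-eclampsia, so it carries the same condition.

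None of the 16 exclusions in 6.2 names hypertension. On drugs to be avoided once pregnancy is confirmed, 5.7 says: "In this particular patient group this may for example include anticoagulation treatment (such as warfarin) or certain types of blood pressure medications".

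The glossary's features of placental insufficiency do not depend on when hypertension began. They are non-reassuring fetal surveillance, abnormal Doppler, oligohydramnios, or "a postnatal birth weight less than the 10th percentile for the gestational age".

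**The concern.** A woman with chronic hypertension can enrol. Suppose she develops new proteinuria, raised transaminases or thrombocytopenia at 29 weeks and is delivered for that reason. Her hypertension did not develop after 20 weeks, so on the printed wording she does not have pre-eclampsia. If no placental feature contributed to the delivery, her birth falls under the rule on other reasons and she is scored as event-free.

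This matters in two ways. Some placenta-mediated outcomes that the trial aims to prevent may be left out of its primary endpoint. And event status depends on the reader: a site that applies the printed text records no event, while a site that follows its own clinical reading of international criteria records one.

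**Working it through.** **Step 1. Trace the case through the text.**
- Eligible? Yes: hypertension is not an exclusion (6.2).
- Pre-eclampsia? Not on the literal wording (glossary, 8.2).
- Eclampsia? No rescue, because it is defined through pre-eclampsia.
- Placental insufficiency? Yes, if the birth was due to one of the listed features. Only deliveries indicated purely by maternal disease are lost.
- Otherwise: a preterm birth for other reasons, so not an event.

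Section 4.1.1 prints a different endpoint, naming fetal growth restriction or stillbirth in place of placental insufficiency. The alternative route would then be narrower. That conflict is a separate matter and needs reconciling in its own right.

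**Step 2. Reproduce the planned sample size (10.2).** Inputs: 63% versus 47%, alpha 0.05 (taken as two-sided), power 80%, crossover 5%.
- One-way crossover moves 0.47 to 0.47 + 0.05 × 0.16 = 0.478.
- n per arm = (1.960 + 0.842)² × (0.63 × 0.37 + 0.478 × 0.522) / 0.152² = 164 after rounding up.
- Total = 328, as stated. The sample size is not in question.

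**Step 3. Planned events.** 164 × 0.63 + 164 × 0.47 = 103 + 77 = about 180.

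**Step 4. Births at issue.** The Protocol gives no rate. Assumptions: 5 to 15% of women have chronic hypertension, and 10 to 20% of these deliver before 34 weeks for superimposed pre-eclampsia.
- Low: 328 × 0.05 × 0.10 = about 2.
- High: 328 × 0.15 × 0.20 = about 10.
- Share of planned events: 2/180 = 1.1% to 10/180 = 5.5%.

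These are upper figures, because births that count through placental insufficiency have not been subtracted.

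**Step 5. Effect on power.** Assume the same share f of events is missed in each arm, so both rates are multiplied by (1 − f). Power is for 164 per arm, two-sided 0.05, pooled variance under the null.

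| f | Rates | Difference | Power, no crossover | Power, 5% one-way crossover |
|---|---|---|---|---|
| 0 | 63.0% v 47.0% | 16.0 points | 83.3% | 79.4% |
| 1% | 62.4% v 46.5% | 15.8 points | 82.4% | 78.4% |
| 5% | 59.9% v 44.7% | 15.2 points | 79.0% | 74.7% |
| 10% | 56.7% v 42.3% | 14.4 points | 74.4% | 69.9% |

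With f = 0 and crossover, power is 79.4% rather than 80% because this formula pools the variance, whereas 328 comes from the unpooled one.

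The risk ratio stays at 0.47/0.63 = 0.746 when f is equal in both arms. The risk difference shrinks and precision falls.

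**The case against.** The strongest reply is that the composite already has a broad second route. Many superimposed cases will show growth restriction, abnormal Doppler or another listed feature that led to delivery, and these are events whatever the onset of hypertension. This stands. A reader might infer that every such birth is scored as a success, and the text does not support that.

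Second, the Protocol never says superimposed disease is to be rejected. It is silent, and it refers to international criteria. This stands in part. The reference points back to the glossary, and 8.2 repeats the restrictive wording, so it does not settle the case and leaves two defensible readings.

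Third, a reader might infer from the flowchart in 4.3, which lists "Blood pressure & Pulse" and urine dip only at screening, that the trial's data could never resolve these cases. That goes too far. Medical history and blood pressure are taken at screening, each drug is recorded with its indication (5.7), blood count, kidney and liver function are tested every trimester, maternity records are already used (7.1), and there is a dedicated database section for adverse pregnancy outcomes (9.2.1). The cases are recoverable.

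Fourth, the trial is double-blind and minimised on centre, so differences in how sites read the definition should be similar across arms. This stands: no bias toward either arm is to be expected.

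**Conclusion.** The point holds in limited form. The printed definition has no clause for hypertension present before 20 weeks although such women are eligible. Taken literally, it drops births before 34 weeks indicated purely by maternal superimposed pre-eclampsia. The reference to international criteria lets sites score such a case either way.

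The number affected is unknown and probably small: at most about 2 to 10 pregnancies, or 1 to 6% of about 180 planned events, before subtracting those counted through placental insufficiency. Losing 1% of events costs about 1 point of power, and losing 5% costs 4 to 5 points. The count rests on two assumed rates that the Protocol does not give. The power figures also assume that an equal share of events is missed in each arm, which need not hold if hydroxychloroquine acts differently on this outcome than on the rest of the composite.

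The consequence is inconsistent scoring with some loss of events and power. The documents do not support a conclusion that the treatment comparison is distorted.

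**What to change.** Add one clause to the endpoint definition in the glossary and in 8.2: for endpoint scoring, in a woman with hypertension before 20 weeks, pre-eclampsia is counted when one or more of the listed new-onset conditions develops after 20 weeks. This concerns classification only and changes no clinical care.

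Settle the clause before outcomes are compared by arm, and apply it also to births before 34 weeks that are already recorded, using existing history, medication and maternity records. For each such birth, record on the adverse pregnancy outcomes form whether hypertension pre-dated 20 weeks and which criterion was met.

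The cost is a short amendment, two items on the form and a small amount of retrospective data entry. No visit or test is added.
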